5.0 TREATMENT PROGRAM

Dexrazoxane will be administered per institutional standard during all anthracycline-containing courses of this protocol

5.1 Induction 1 – ADE (10+3+5) with GO

The following therapy guidelines are for patients during Induction I. Patients on Induction I will receive gemtuzumab in addition to ADE therapy based on GO genotyping. Induction I lasts a total of 28 days.

Intrathecal Cytarabine: IT

Given at time of diagnostic lumbar puncture or Day 1.

Age-based dosing:

Age (yrs)	Dose
0-0.99	20 mg
1-1.99	30 mg
2-2.99	50 mg
≥ 3	70 mg

For CNS positive patients: add twice weekly IT AraC doses until CNS is clear, plus two additional treatments. A minimum of four intrathecal treatments are to be administered during the period of three weeks following diagnosis.

Cytarabine: Slow IV Push (e.g., over 1-2 minutes)

100 mg/m²/dose (3.3 mg/kg/dose if BSA < 0.6 m²) every 12 hours (total of 20 doses) on Days 1-10.

Daunorubicin (DAUN): IV over 15 minutes

50 mg/m²/dose (1.67 mg/kg/dose if BSA < 0.6 m²) every other day (total of 3 doses) on Days 1, 3, 5.

See Section 6 if direct bilirubin is > 2.

Etoposide (ETOP): IV over 60 – 120 minutes

100 mg/m²/dose (3.3 mg/kg/dose if BSA < 0.6 m²) daily (total of 5 doses) on Days 1-5.

See Section 6 if direct bilirubin is > 2.

Gemtuzumab Ozogamicin (GO): IV over 2 hours

3 mg/m²/dose (0.1 mg/kg/dose if BSA < 0.6 m²) once (total of 1 dose) on Day 6 through 10.

GO to be given once when GO genotyping demonstrates CC genotype. It can be given on any day between days 6-10 of Induction 1.

Pre-medicate with an antihistamine such as diphenhydramine, 1 mg/kg IV (max 50 mg), acetaminophen 10-15 mg/kg PO (max 650 mg) and methylprednisolone (1mg/kg) PO/IV. Repeat every 4 hours as needed to prevent post infusion complications.

Following Induction I, the next course (Induction II) starts on Day 29 or when blood count parameters and clinical condition are acceptable (whichever occurs later). This should not precede the end of course marrow exam.

5.2 Induction 1 for FLT3-ITD patients – ADE (10+3+5) with GO with Sorafenib

The following therapy guidelines are for patients during Induction I with FLT3-ITD mutation. Patients on Induction I will receive gemtuzumab in addition to ADE therapy based on GO genotyping. Induction I lasts a total of 28 days.

Intrathecal Cytarabine: IT

Given at time of diagnostic lumbar puncture or Day 1.

Age-based dosing:

Age (yrs)	Dose
0-0.99	20 mg
1-1.99	30 mg
2-2.99	50 mg
≥ 3	70 mg

For CNS positive patients: add twice weekly IT AraC doses until CNS is clear, plus two additional treatments. A minimum of four intrathecal treatments are to be administered during the period of three weeks following diagnosis.

Cytarabine: Slow IV Push (e.g., over 1-2 minutes)

100 mg/m²/dose (3.3 mg/kg/dose if BSA < 0.6 m²) every 12 hours (total of 20 doses) on Days 1-10.

Daunorubicin (DAUN): IV over 15 minutes

50 mg/m²/dose (1.67 mg/kg/dose if BSA < 0.6 m²) every other day (total of 3 doses) on Days 1, 3, 5.

See Section 6 if direct bilirubin is > 2.

Etoposide (ETOP): IV over 60 – 120 minutes

100 mg/m²/dose (3.3 mg/kg/dose if BSA < 0.6 m²) daily (total of 5 doses) on Days 1-5.

See Section 6 if direct bilirubin is > 2.

Gemtuzumab Ozogamicin (GO): IV over 2 hours

3 mg/m²/dose (0.1 mg/kg/dose if BSA < 0.6 m²) once (total of 1 dose) on Day 6 through 10.

GO to be given once when GO genotyping demonstrates CC genotype. It can be given on any day between days 6-10 of Induction 1.

Pre-medicate with an antihistamine such as diphenhydramine, 1 mg/kg IV (max 50 mg), acetaminophen 10-15 mg/kg PO (max 650 mg) and methylprednisolone (1mg/kg) PO/IV. Repeat every 4 hours as needed to prevent post infusion complications.

Sorafenib (SORAF): PO

Days: 11 through 28.

Dose: 200 mg/m²/dose daily, rounded to accommodate tablet size. The maximum dose will be 400 mg. Dose will be administered per dosing nomogram in Appendix I.

Note: Sorafenib tablets should be taken at least 1 hour before or 2 hours after food. Tablets should be taken with clear liquids (approximately 2 to 4 ounces for children < 12 years and 4 to 8 ounces for \geq 12 years). If taken with food, sorafenib should be taken with a moderate to low fat meal. Tablets should not be crushed and should be swallowed whole. However, sorafenib tablets can be dispersed in water to facilitate the administration to subjects that cannot swallow tablets

Following Induction I, the next course (Induction II) starts on Day 29 or when blood count parameters and clinical condition are acceptable (whichever occurs later). This should not precede the end of course marrow exam.

5.3 Induction II – MA

The following therapy guidelines are for patients during Induction II. Induction II lasts 28 days or longer.

Progression to Induction II should await disease response determination (MRD and extramedullary disease) in order to correctly assign risk stratum. Patients with high or low risk cytogenetic/molecular features may proceed on to Induction II therapy before disease response results are available. By the beginning of Induction II, patients should have been classified as Low or High risk. **If a patient is classified as High risk at the end of Induction I and no family HLA match is found, initiation of an unrelated donor search should occur.**

Intrathecal Cytarabine (IT ARAC): IT

IT ARAC may be administered on Day 1 of Induction II or with the bone marrow evaluation at the end of Induction I.

Age-based dosing:

Age (yrs)	Dose
0 - 0.99	20 mg
1 - 1.99	30 mg
2 - 2.99	50 mg
\geq 3	70 mg

For newly detected CNS positive patients who were CNS negative at diagnosis: IT cytarabine is to be administered twice weekly until the CSF is clear. A minimum of 4 intrathecal treatments must be given and a maximum of 6 intrathecal treatments may be given. Patients whose CSF is clear at the second spinal tap will receive 3 intrathecal treatments once the CSF is clear and all other patients will receive 2 intrathecal treatments once the CSF is clear. Patients with refractory CNS leukemia following 6 doses of therapy will be taken off protocol therapy.

High Dose Cytarabine (HD ARAC): IV over 1 - 3 hours

Days: 1 through 4.

Dose: 1000 mg/m²/dose, every 12 hours (i.e., 2000 mg/m²/day, divided BID) or 33 mg/kg/dose, every 12 hours (i.e., 66 mg/kg/day, divided BID) if BSA < 0.6 m².

Suggested premedications and supportive care: Administer steroid eye drops (0.1% dexamethasone or 1% prednisolone ophthalmic solution), 2 drops to each eye every 6 hours, beginning immediately before the first dose and continuing for 24 hours after the last dose. If patient does not tolerate steroid eye drops, may administer artificial tears on an every 2-4 hour schedule.

Patients in whom serum creatinine is > 2 mg/dL or > 2 x normal for age, must have a CrCl performed (Day 1) and doses of cytarabine adjusted as outlined.

MitoXANTRONE (MITOX): IV over 15 - 30 minutes

Days: 3 through 6.

Dose: 12 mg/m²/dose or

0.4 mg/kg/dose if BSA < 0.6 m².

Note: Administer through the tubing of a rapidly infusing solution of D5W or 0.9% NaCl. Avoid extravasation; the use of a central line is suggested. On the Days 3 and 4, mitoXANTRONE should be given 8 hours after the 5th and 7th high dose cytarabine infusions are complete.

Patients with high risk status may proceed to best allogenic donor SCT or alternative donor SCT following Induction II. Depending on timing, these patients may receive a third course of chemotherapy (Intensification I) prior to HSCT. This course could be either AE or HD ARAC/LASP.

Patients with low risk status who had low risk markers and were MRD positive at the end of Induction I and continue to be MRD positive after Induction II will come off protocol.

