Patients with low-risk AML have favorable outcomes (3-year EFS and OS - 70% and 85% respectively) as compared to patients with high-risk AML (3-year EFS and OS – 30% and 48% respectively)¹. Regardless of risk, disease relapse still remains the major cause of mortality¹. Anthracyclines comprise an important component of relapsed AML therapy and higher doses of anthracyclines received in upfront AML therapy preclude their use at the time of relapse¹⁰. Given the concerns for long term toxicity without clear evidence of benefit to additional anthracyclines and etoposide in low-risk AML patients, we chose to adopt an institutional approach (Aflac-AML regimen) whereby newly diagnosed low-risk AML patients were treated with four cycles of chemotherapy that was identical to the high-risk group per AAML1031 which received chemotherapy alone. The aim of our regimen was to limit anthracycline exposure to 342 mg/m² and etoposide exposure to 1.25 g/m² in low-risk AML patients while maintaining the same favorable outcomes. A comparison of the two regimens is outlined in the table (Table 1) below.

Table 1: Therapy regimen for Aflac-AML, AAML0531 and AAML1031 low-risk patients

[figure not shown]
Aflac-AML		COG AAML0531		COG AAML1031	
Induction 1					
Cytarabine	100 mg/m ² /dose every 12 hours IV Days 1-10	Cytarabine	100 mg/m ² /dose every 12 hours IV Days 1-10	Cytarabine	100 mg/m ² /dose every 12 hours IV Days 1-10
Daunorubicin	50 mg/m ² /dose IV Days 1, 3, 5	Daunorubicin	50 mg/m ² /dose IV Days 1, 3, 5	Daunorubicin	50 mg/m ² /dose IV Days 1, 3, 5
Etoposide	100 mg/m ² /dose IV Days 1-5	Etoposide	100 mg/m ² /dose IV Days 1-5	Etoposide	100 mg/m ² /dose IV Days 1-5
Induction 2					
Cytarabine	1,000 mg/m ² /dose every 12 hours IV Days 1-4	Cytarabine	100 mg/m ² /dose every 12 hours IV Days 1-8	Cytarabine	100 mg/m ² /dose every 12 hours IV Days 1-8
Mitoxantrone	12 mg/m ² /dose IV Days 3-6	Etoposide	100 mg/m ² /dose IV Days 1-5	Etoposide	100 mg/m ² /dose IV Days 1-5
----	----	Daunorubicin	50 mg/m ² /dose IV Days 1, 3, 5	Daunorubicin	50 mg/m ² /dose IV Days 1, 3, 5
Intensification 1					
Cytarabine	1,000 mg/m ² /dose every 12 hours IV Days 1-5	Cytarabine	1,000 mg/m ² /dose every 12 hours IV Days 1-5	Cytarabine	1,000 mg/m ² /dose every 12 hours IV Days 1-5
Etoposide	150 mg/m ² /dose IV Days 1-5	Etoposide	150 mg/m ² /dose IV Days 1-5	Etoposide	150 mg/m ² /dose IV Days 1-5
Intensification 2					

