10.1 CRITERIA FOR REMOVAL FROM PROTOCOL THERAPY AND OFF STUDY CRITERIA

10.2 Criteria for Removal from Protocol Therapy

1. Failure to attain or maintain remission following Induction II ($\geq 5\%$ malignant blasts or extramedullary disease).
2. Relapse after Induction II of any site following remission.
3. Refractory CNS leukemia following 6 doses of IT cytarabine therapy in Induction I or Induction II.
4. CNS leukemia at start of Induction II after treatment for CNS leukemia in Induction I.
5. Grade 3 or greater neurotoxicity from HD cytarabine or,

6. Other intolerable or unacceptable toxicity secondary to the standard chemotherapy backbone.
7. Refusal of further protocol therapy by patient/parent/guardian.
8. Completion of planned therapy.
9. Physician determines it is in patient's best interest.
10. Development of a second malignancy.
11. Graft failure

Patients who are off protocol therapy are to be followed until they meet the criteria for Off Study (see below). Follow-up data will be required unless consent was withdrawn.

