10.3 Off Study Criteria

1. Death.
2. Lost to follow-up.
3. Patient enrollment onto another study with tumor therapeutic intent (e.g., at recurrence).*
4. Withdrawal of consent for any further data submission.
5. Tenth anniversary of study entry.
6. Excluded constitutional condition or oncologic diagnosis is indicated following enrollment
7. FLT3/ITD status is unknown at End of Induction I.

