11.1 STATISTICAL CONSIDERATIONS

Sample size: This is a pilot study aimed at utilizing a risk-stratified approach along with pharmacogenomics to treat newly diagnosed patients with AML. Annually we expect to have 10-20 de novo AML patients to be diagnosed and treated at our institution. This two-year study would be expected to enroll approximately 30 patients (both low and high risk) during that time period. As a pilot study, this trial is not hypothesis-driven but rather estimation-driven, and the sample size is based on a feasible two-year target for our institution.

Descriptive statistics will be conducted for demographic and patient characteristic variables, including toxicity related variables. Mean and standard deviation will be used for continuous variables and frequency and percent will be used for categorical variables.

Primary Endpoints:

1. Event-free survival: Event-free survival (EFS) is defined as the time from on study to death, failure to achieve remission or relapse, where those patients who do not experience these events will be censored at last follow-up date. EFS will be estimated using the Kaplan-Meier method for newly diagnosed patients with pediatric acute myeloid leukemia using a risk stratified approach.

Secondary Endpoints:

1. Disease-free survival: Disease-free survival (DFS) from end of first course of therapy is defined as time from end of first course of therapy to death or relapse, where those patients who do not experience these events will be censored at last follow-up date. DFS will be estimated using the Kaplan-Meier method for newly diagnosed patients with pediatric acute myeloid leukemia using a risk stratified approach.
2. Overall survival: Overall survival (OS) is defined as (1) time from study entry and (2) from end of first course of therapy to death, where those who do not die will be censored at

last follow-up date. OS will be estimated using the Kaplan-Meier method for newly diagnosed patients with pediatric acute myeloid leukemia using a risk stratified approach.

3. Minimal residual disease: Minimal residual disease (MRD) is the proportion of patients that are in remission (MRD negative) after one cycle of induction chemotherapy in both the GO and non-GO groups. Descriptive statistics (frequency and percent) will be used to estimate the frequency of MRD.

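### As the visible text stands, entry to another therapeutic study ends follow-up (10.3 item 3), so relapsed patients who join one are censored alive for OS, probably biasing it modestly upward

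*Combined protocol and SAP*

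**What the plan says.** Four pieces of text have to be read together.

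- **Section 10.2, closing paragraph.** "Patients who are off protocol therapy are to be followed until they meet the criteria for Off Study". The next sentence asks for follow-up data from everyone who has not withdrawn consent.
- **Section 10.3, item 3.** One off-study criterion is "Patient enrollment onto another study with tumor therapeutic intent (e.g., at recurrence"). An asterisk follows, but its note is not in the text available. Withdrawal of consent is a separate criterion (item 4), and the tenth anniversary of study entry is another (item 5).
- **Section 11.1, OS.** OS runs from study entry and also "from end of first course of therapy to death, where those who do not die will be censored at" the last follow-up date.
- **Section 11.1, EFS.** Events are death, failure to achieve remission and relapse, "where those patients who do not experience these events will be censored at last follow-up date".

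Section 5.3 bears on a narrower case. Patients with low-risk markers who "were MRD positive at the end of Induction I and continue to be MRD positive after Induction II will come off protocol". Section 10.2 item 1 describes "Failure to attain or maintain remission following Induction II" by a blast count of 5% or more, or extramedullary disease. Section 11.1 writes "in remission (MRD negative) after one cycle of induction chemotherapy" for the separate course-1 response endpoint.

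**The concern.** Kaplan-Meier treats a censored patient as having the same later risk as those still being followed. Item 3 breaks that assumption for OS. The trigger for leaving follow-up is entry to another treatment study, and the protocol's own example is recurrence. A child who relapses and joins a relapse trial has a much higher risk of death than the children who remain, yet leaves the OS analysis alive, and a later death is never counted. The likely direction of bias is upward.

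Section 11.1 describes the trial as driven by estimation, not by a hypothesis. No test or threshold turns on OS, but the estimate is itself the result. The confidence interval does not account for this bias.

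**Working it through.** **The plan's own figure.** Two years at 10 to 20 patients a year is 20 to 40; the midpoint is 2 × 15 = 30, which agrees with the stated target of about 30. The plan gives no precision for OS or EFS and no count of patients expected to enter another study.

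**The chain for OS.**
1. The patient relapses. This is an EFS event and, under 10.2, a reason to stop protocol therapy. Follow-up continues.
2. The patient enters another therapeutic study. Item 3 of 10.3 is met, so the follow-up required by 10.2 ends.
3. Section 11.1 censors OS at last follow-up, with the patient alive.
4. No visible section provides for survival follow-up after off study.

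**Inputs for size.** EFS of about 50% and OS of about 65% come from the protocol's opening summary. The 3-year horizon, the number entering another study and the split of first events are assumptions.

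**Survival after the event.**
- If every first event is a relapse: (0.65 − 0.50)/0.50 = 30%.
- Some first events are deaths, and those patients cannot enroll elsewhere. If 10 of the 50 points are deaths, 40 points are relapses, and survival after relapse is (0.65 − 0.50)/0.40 = 37.5%.

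**Approximate bias per patient.** Censoring hands the patient's weight to those still at risk, so the bias is about (OS of those still at risk − own survival)/30. OS among those still at risk is at least 65%, because they have already survived to that time; I take 65% to 80% as an assumed range.
- Low end: (0.65 − 0.375)/30 = 0.9 points.
- High end: (0.80 − 0.30)/30 = 1.7 points.

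**Simulation of Kaplan-Meier OS at 3 years**, with first events either exponential or all within 18 months, and three of 30 patients censored:

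| Assumption | Rise in OS estimate |
|---|---|
| All first events are relapses | 4.3 to 4.9 points |
| 10 of the 50 points are first-event deaths | 3.6 to 4.2 points |
| As above, with a 3-month lag to enrollment | 3.4 to 3.6 points |
| Nobody enters another study | 0 |

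Per patient this is 3.4/3 = 1.1 to 4.9/3 = 1.6 points, inside the hand-calculated bracket.

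**OS half-width at n = 30.** 1.96 × √(0.65 × 0.35/30) = 17.1 points.

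**EFS.** A patient who enters another study at relapse has already been counted. The remaining case is a 5.3 patient with under 5% blasts and no extramedullary disease who enters another study before relapse or death, with remission not read as MRD negative. The bias is (EFS of others − own EFS)/30, with EFS of others 50% to 70%:
- Own EFS 50%: 0 to 0.7 points.
- Own EFS 30%: (0.50 − 0.30)/30 = 0.7 to (0.70 − 0.30)/30 = 1.3 points.
- Own EFS 0%: 1.7 to 2.3 points.
- Own EFS equal to that of the others: zero.

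The 30% is the 3-year high-risk figure in Section 2.1.1; 5.3 patients are classed as low risk, so it may be too pessimistic. The EFS half-width is 1.96 × √(p(1 − p)/30) = 16.4 points at p = 0.7 and 17.9 at p = 0.5.

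**The case against.** The strongest objection is the asterisk. The source attaches a note to exactly this rule, the note is not in the text available, and it may say that survival follow-up continues. This stands as a condition on the whole point: the sponsor should check the note first. It does not refute the point, because the visible rule, followed as written, ends follow-up.

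A second objection is that 10.2 requires follow-up data from all who have not withdrawn consent, and 10.3 allows follow-up to ten years. Both suggest an intent to follow patients for a long time. But the sentence in 10.2 comes directly after the limit set by the off-study criteria and does not say that it reaches past them.

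A third is that the size is speculative. That is fair. No document says how many patients would enter another study, and even five of 30 would move OS by less than its half-width.

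A reader might infer more than the documents support:
- *That removal under 5.3 itself censors patients.* It does not. Coming off protocol therapy leaves the patient in follow-up under 10.2, and persistent MRD is not an off-study criterion in 10.3.
- *That the primary endpoint is materially biased.* Relapse is an EFS event. The remaining EFS path needs several conditions together, and nothing shows that any patient will meet them.
- *That the two uses of the word remission are a contradiction.* The MRD-negative wording belongs to the course-1 response endpoint, and a morphologic rule for EFS is a legitimate choice. Saying which applies is a clarification.

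**Conclusion.** The point holds for OS, on condition that the unseen note to item 3 does not keep survival follow-up. As written, relapsed patients who join another therapeutic study are censored alive, the censoring is informative, and Kaplan-Meier OS is probably too high. The size is modest: about 3.4 to 4.9 points if three of 30 patients are affected and zero if none are. This rests on EFS 50%, OS 65%, a 3-year horizon and an assumed count.

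The effect on EFS is slight: 0 to 2.3 points for each 5.3 patient who enters another study before relapse, against a half-width of 16 to 18 points. The change is worth making because it is cheap and the trial's output is its estimates. It does not call the design into question. Confidence is medium because of the missing note.

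**What to change.** First confirm what the asterisk on 10.3 item 3 says. If it does not already do so, amend item 3 so that entry to another therapeutic study ends protocol data submission, but relapse and survival status are still collected, consent permitting, to the tenth anniversary of study entry. In 11.1, censor OS and EFS at the last date on which status is known. This closes both paths. It should be done before patients go off study, since status not collected then may not be recoverable.

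As a clarification only, state in 11.1 which definition of remission applies to the EFS event. I would not add an analysis that scores persistent MRD as an event: it would apply an event rule to low-risk-marker patients that high-risk patients do not have.

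The cost is a line in each section, a little more follow-up work, and consent wording that covers it. OS will then include the effect of later treatment and may look slightly less favorable.

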5.4 Induction II for FLT3-ITD patients – MA with Sorafenib

The following therapy guidelines are for patients during Induction II with FLT3-ITD AML. Induction II lasts 28 days or longer.

Progression to Induction II should await disease response determination (MRD and extramedullary disease) in order to correctly assign risk stratum. Patients with high or low risk cytogenetic/molecular features may proceed on to Induction II therapy before disease response results are available. By the beginning of Induction II, patients should have been classified as Low or High risk. **If a patient is classified as High risk at the end of Induction I and no family HLA match is found, initiation of an unrelated donor search should occur.**

Intrathecal Cytarabine (IT ARAC): IT

IT ARAC may be administered on Day 1 of Induction II or with the bone marrow evaluation at the end of Induction I.

Age-based dosing:

Age (yrs)	Dose
0 - 0.99	20 mg
1 - 1.99	30 mg
2 - 2.99	50 mg
≥ 3	70 mg

For newly detected CNS positive patients who were CNS negative at diagnosis: IT cytarabine is to be administered twice weekly until the CSF is clear. A minimum of 4 intrathecal treatments must be given and a maximum of 6 intrathecal treatments may be given. Patients whose CSF is clear at the second spinal tap will receive 3 intrathecal treatments once the CSF is clear and all other patients will receive 2 intrathecal treatments once the CSF is clear. Patients with refractory CNS leukemia following 6 doses of therapy will be taken off protocol therapy.

High Dose Cytarabine (HD ARAC): IV over 1 - 3 hours

Days: 1 through 4.

Dose: 1000 mg/m²/dose, every 12 hours (i.e., 2000 mg/m²/day, divided BID) or 33 mg/kg/dose, every 12 hours (i.e., 66 mg/kg/day, divided BID) if BSA < 0.6 m².

Suggested premedications and supportive care: Patients in whom serum creatinine is > 2 mg/dL or > 2 x normal for age, must have a CrCl performed (Day 1) and doses of cytarabine adjusted as outlined.

MitoXANTRONE (MITOX): IV over 15 - 30 minutes

Days: 3 through 6.

Dose: 12 mg/m²/dose or 0.4 mg/kg/dose if BSA < 0.6 m².

Note: Administer through the tubing of a rapidly infusing solution of D5W or 0.9% NaCl. Avoid extravasation; the use of a central line is suggested. On the Days 3 and 4, mitoXANTRONE should be given 8 hours after the 5th and 7th high dose cytarabine infusions are complete.

Sorafenib (SORAF): PO

Days: 7 through 34.

Dose: 200 mg/m²/dose daily, rounded to accommodate tablet size. The maximum dose will be 400 mg.

Dose to be administered per dosing nomogram in Appendix I.

Note: Sorafenib tablets should be taken at least 1 hour before or 2 hours after food. Tablets should be taken with clear liquids (approximately 2 to 4 ounces for children < 12 years and 4 to 8 ounces for \geq 12 years). If taken with food, sorafenib should be taken with a moderate to low fat meal. Tablets should not be crushed and should be swallowed whole. However, sorafenib tablets can be dispersed in water to facilitate the administration to subjects that cannot swallow tablets.

Patients with FLT3-ITD AML may proceed to best allogenic donor SCT or alternative donor SCT following Induction II. Depending on timing, these patients may receive a third course of chemotherapy (Intensification I) prior to HSCT. This course could be either AE or HD ARAC/LASP with sorafenib.

